## SPECIFIC AIMS

Hundreds of thousands of people annually suffer from compromised nutrition, hydration, and quality of life due to impaired swallowing (oropharyngeal dysphagia or OPD), and aspiration of swallowed food into the respiratory system. OPD leads to aspiration pneumonia (AP) which increases the risk of death during hospitalization threefold, and adds 53,000 annual hospitalization days and nearly \$550 million to US health care costs annually. Through our research, we seek to pre-emptively prevent OPD diagnoses from evolving into aspiration pneumonia, and mitigate these economic and human costs. Gold-standard videofluoroscopy (VF), used to objectively diagnose OPD, is not an appropriate screening tool due to its invasiveness, size and prohibitive cost, and it cannot be deployed immediately upon suspicion of OPD. Standard institutional screening (SIS) protocols are therefore used to predict OPD. But since they rely solely on subjective, non-instrumented human judgment of OPD risk by simply watching the patient swallowing and observing for choking, a) their sensitivity is compromised because half of aspirators do not choke due to silent aspiration, b) their specificity is compromised because up to 60% of nonaspirators cough during SIS, and c) in settings in which subsequent VF is not available or feasible, SIS provide no diagnostic information to guide intervention because they cannot identify the swallowing impairments leading to aspiration.

In our current NIH-funded effort (**for which the PI received the Presidential Early Career Award for Scientists and Engineers in 2016**), we have developed an instrumental tool that can noninvasively identify patients with OPD with high agreement with gold standard VF, through innovative *high-resolution cervical auscultation* (HRCA) methods. Through collection of concurrent VF and HRCA data from 274 patients and using advanced data analytics methods, we showed that HRCA can accomplish two outcomes previously only possible with VF: a) differentiate between severe aspiration and unimpaired swallowing in patients with suspected OPD, and b) detect kinematic components of abnormal swallowing physiology that lead to aspiration. Our next major step is to translate these advances into an objective, precise instrumental screening tool that significantly increases accuracy of SIS in a convenient and easily adoptable form factor. There are three gaps we need to address to accomplish these goals. We need to finish characterizing the entire range of swallowing function from unimpaired through severe OPD using HRCA as our HRCA research has relied on data from patients with OPD. We then need to equate HRCA predictions to validated gold-standard derived cutoffs of OPD severity, and finally to combine these results into a deployable tool that can be tested clinically. Therefore, we propose research leading to novel clinical and engineering advances that position our HRCA tool to accurately identify silent aspiration and OPD to enable patients to be immediately triaged for treatment to prevent AP and related adverse events, and prevent unnecessary treatment to unimpaired people.

**AIM 1: Complete collection of the entire continuum of HRCA swallowing signals from unimpaired to severely impaired, by collecting HRCA swallow data from healthy people. Hypothesis: HRCA signal signatures of swallowing in unimpaired people are distinguishable and significantly different discriminating from swallows from people with OPD.** The aim will dramatically improve screening accuracy by completing characterization of the entire HRCA OPD severity continuum from unimpaired to severely impaired.

**AIM 2: Translate and equate HRCA swallow signal signatures to validated measures of swallowing impairment. Hypothesis: HRCA cutoffs will be significantly associated with validated VF-derived OPD impairment cutoffs.** Accomplishment of this aim positions us to establish independent HRCA cutoffs for levels of OPD severity that differentiate clinically significant OPD and aspiration from benign swallowing impairments.

**AIM 3: Prospectively assess the effectiveness of our HRCA system in predicting clinically significant OPD and aspiration in a randomized, controlled trial. Hypothesis: HRCA, will detect significantly more OPD and significantly more non-OPD, compared to SIS alone.** For this major step, we will deploy combinations of HRCA and SIS with consenting patients, and compare all screening predictions (SIS, HRCA, SIS + HRCA) to VF data from all participants.

[figure not shown]
The outcome of this research will be a clinically accurate, inexpensive, and noninvasive HRCA screening tool that will fundamentally advance efforts to reduce morbidity and mortality caused by OPD. The positive translational impact of this work is the melding of engineering (HRCA) with the clinical (SIS) screening processes. This major technological leap will elevate the current standard of patient care by ensuring that patients with OPD are correctly identified before adverse events can occur, patients without OPD are not unnecessarily deprived of food more accurately than current methods, as well as lowering health care expenditures and lengths of stay and improving quality of lives.

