**Table 2 –** Frequency of signal maxima co-occurring with swallow kinematic events; separated by PAS ranges PAS 1-2 vs. PAS 3-8. NUME denotes the number of signal maxima co-occurred with swallow kinematic events > 50% of the time. MIC denotes a microphone, while S-I, A-P, and M-L denote vibrations in superior-inferior, anterior-posterior, and medial-lateral directions captured by an accelerometer.

Sensor	NUME	PAS 1-2		PAS 3-8	
		overall %	range	overall %	range
MIC	80/91	49	37-65	13.6	10-18
S-I	64/91	45	29-62	11	7-16
A-P	55/91	43	26-62	11	6-17
M-L	48/91	40	25-61	10	3-16

**A2.d. Experimental approach:** STEP 1: All swallows from patients and healthy participants (Aim 1) will be rated using the MBSImP. Judges will undergo standardized training in visual inspection and MBSimP ratings of swallow kinematic functions and impairments, and establishment of inter- and intra-rater reliability before beginning scoring. STEP 2: In addition to MBSimP component 16 (pharyngeal residue), pharyngeal residue (valleculae, pyriform sinuses) will be measured using the Normalized Residue Rating Scale which standardizes areas of barium residue retained in pharyngeal recesses (valleculae, pyriform sinuses) using conversion factors based on individual patient height [112]. STEP 3: We will measure airway compromise using the PAS [109]. STEP 4: Pre-process HRCA recordings per steps taken in previous publications [29, 30, 71] to remove any disturbances and diminish noise in these recordings.

STEP 5: We will develop an algorithm based on the state-of-the-art machine learning concepts whose output will be the differentiation between healthy controls and people with suspected dysphagia whose swallows did not exhibit dysphagia, healthy dysphagic (see Figure 11). Specifically, we will utilize a random 70% training subsample for the deep belief machine learning approach as in our preliminary works [70], and once modeling is complete, use the remaining 30% validation subsample to obtain accuracy estimates devoid of model overfitting.

**A2.e. Data interpretation:** We will employ the same deep learning methods as in Aim 1 for our primary analysis, but instead will employ techniques suitable for categorical, ordinal dependent variables such as MBSimP and PAS. In addition, we will employ regression tree and linear mixed model methods in an effort to obtain simpler

**Figure 11 –** Our proposed experimental and data analysis approach for Aim 2.

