means of converting HRCA signals. We will examine performance metrics such as root mean square error and multiple coefficient of determination ( $R^2$ ) to evaluate our score equating models.

**A2.f. Expected outcomes:** The benchmark for success of Aim 2 will be creation of a set of HRCA signal signatures that can be translated to MBSImP, PAS, and pharyngeal retention measures. We anticipate a model can be built with sufficiently high predictive ability so that  $R^2$  and/or root mean square error of score translation is no greater than 5% of the range of the swallowing impairment measure. The major outcome of this aim is that HRCA signal signatures will reflect swallow kinematic and airway protection function and equate to standard measures of swallow impairment which will help us develop the HRCA based Aspirometer as a tool that characterizes and predicts risk of adverse outcomes associated with dysphagia, without imaging.

**A2.g. Challenges and contingency plans:** As in Aim 1, in the highly unlikely event that our VF judges' ratings drift unacceptably, we will increase surveillance on inter- and intra-rater reliability and pull judges from analysis and retrain them to criterion, retest their reliability before placing them back online.

**A2.h. Sample size justification:** The proposed approach is based on nonlinear modeling for which classical sample size calculation procedures are not suitable [125, 126]. As our augmented dataset is expected to contain more than 4000 (existing recordings)+700 (Aim 1) swallows, we strongly believe that it is a sufficient number of swallows as previous publications using similar nonlinear modeling techniques used data sets with a significantly lower number of samples [127-129]. Nonetheless, accounting for an intra-class correlation of 0.7 and a resulting design effect of 3.8 as in Aim 1, and assuming as many as 20 predictors will be needed in a linear model, we will be able to detect statistical significance of an  $R^2$  as small as 0.03 in the training sample and 0.06 in the validation sample with 80% power at  $\alpha=0.05$ .

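### Aim 2 states a hypothesis about cutoffs, but A2.d to A2.h name no VF cutoff, derive no HRCA cutoff and specify no test linking the two

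*Combined protocol and SAP*

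**What the plan says.** **Hypothesis and purpose.** The Specific Aims state the Aim 2 hypothesis as "HRCA cutoffs will be significantly associated with validated VF-derived OPD impairment cutoffs". They list this as one of the gaps to close ("We then need to equate HRCA predictions to validated gold-standard derived cutoffs of OPD severity") and say that completing the aim "positions us to establish independent HRCA cutoffs for levels of OPD severity". A2.a gives a different working hypothesis: that HRCA can quantify severity and airway protection comparably to accepted VF-based scales.

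**Models.** A2.e takes deep learning as the primary analysis, with "techniques suitable for categorical, ordinal dependent variables such as MBSimP and PAS". As an addition, "we will employ regression tree and linear mixed model methods in an effort to obtain simpler" conversions of the signals. A2.d STEP 5 also plans an algorithm, with accuracy estimated in a 30% validation subsample. Its target is the "differentiation between healthy controls and people with suspected dysphagia whose swallows did not exhibit dysphagia".

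**Success criteria.** A2.e says: "We will examine performance metrics such as root mean square error and multiple coefficient of determination". A2.f sets its numerical benchmark on R-squared and/or RMSE, with 5% of the range of the impairment measure as the limit. A2.h gives 80% power for an R-squared of 0.03 in training and 0.06 in validation.

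**Elsewhere.** A1.a plans a cutoff for normal swallows. A1.e plans a confusion matrix with sensitivity and specificity, and A1.f expects over 90% accuracy for PAS 1-2. All of this is under Aim 1.

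**The concern.** A hypothesis about cutoffs needs three things in the analysis section: the reference cutoffs on the VF scales, a rule that fixes the HRCA cutoffs, and a measure or test of how well they agree. Section A2 supplies none of them. It judges how closely predicted scores track observed scores on average.

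These are different questions. RMSE and R-squared average over the whole scale and treat a step from PAS 1 to 2 like a step from 2 to 3, although only the second crosses the line that A2.c uses between normal and abnormal airway protection. A2.e itself calls the ratings ordinal.

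At stake is what Aim 2 can report. If the plan is followed exactly, the Specific Aims hypothesis is neither supported nor refuted. Cutoffs for MBSImP and residue, and for PAS above the 1-2 boundary, could then be picked after the data are seen. The HRCA criteria listed in A3.a, and the algorithm output that A3.d STEP 3 takes from Aims 1 and 2, would draw on Aim 2 results with no tested cutoff.

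**Working it through.** **1. Is a cutoff specified anywhere in A2.d to A2.h?**

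| Section | What it fixes | VF cutoff | HRCA cutoff | Test between them |
|---|---|---|---|---|
| A2.d STEPs 1-4 | MBSImP, residue and PAS ratings; signal pre-processing | none | none | none |
| A2.d STEP 5 | Healthy controls against patients without dysphagic swallows | none on any scale | none stated | accuracy for that contrast only |
| A2.e | Ordinal deep learning; tree and mixed models; RMSE and R-squared as examples | none | none | none |
| A2.f | R-squared and/or RMSE benchmark | none | none | none |
| A2.h | Power for R-squared | none | none | none |

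Both groups in STEP 5 have swallows without dysphagia, so that contrast is not a severity cutoff. A2.c splits PAS at 1-2 against 3-8, but as a preliminary result.

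**2. Reproducing the A2.h figures.** Inputs: 4000 + 650 = 4650 swallows (A1.h, after refusals), design effect 3.8, 20 predictors, alpha 0.05, overall F test.

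- Validation: effective n = 4650 × 0.3 / 3.8 = 367. The R-squared detectable with 80% power is 0.056 with noncentrality f²·n and 0.060 with f²·(n − k − 1). The stated 0.06 reproduces.
- Training: effective n = 4650 × 0.7 / 3.8 = 857. The detectable R-squared is 0.024 to 0.025, so the stated 0.03 errs on the safe side.

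**3. What an R-squared of 0.06 says about a cutoff.** Illustration, not a plan figure. Assumptions:

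- observed score Y and HRCA predictor X are standard bivariate normal with correlation r = √R²;
- the translated score is the least-squares prediction r·X;
- the VF cutoff c is applied unchanged to it;
- 36% of swallows lie beyond c, borrowed from Table 4 (55/154 = 0.357).

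Then c = Φ⁻¹(0.64) = 0.358 and r = √0.06 = 0.245. A swallow is flagged when X > c/r = 1.463.

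- P(flagged) = 0.0717; P(flagged and impaired) = 0.0390.
- Sensitivity = 0.0390 / 0.36 = 0.108.
- Specificity = 1 − (0.0717 − 0.0390) / 0.64 = 0.949.

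A statistically significant R-squared at the powered size is therefore compatible with missing about nine in ten impaired swallows at that cutoff.

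**4. The same calculation if the RMSE benchmark is met.** On PAS the range is 8 − 1 = 7, so 5% is 0.35 points. With R² = 1 − (0.35/SD)² and an assumed PAS SD of 1 to 2.5, R² runs from 0.88 to 0.98.

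| R² | Sens/spec, 20% impaired (assumed) | Sens/spec, 36% impaired |
|---|---|---|
| 0.06 | 0%/100% | 11%/95% |
| 0.88 | 77%/96% | 84%/93% |
| 0.95 | 86%/97% | 90%/95% |
| 0.98 | 92%/98% | 94%/97% |

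The size of the loss thus depends on which of the plan's own targets is reached.

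**The case against.** The other side has several sound arguments.

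- **A2.a's working hypothesis is about comparability of scores**, and translation error does address that. This stands. RMSE and R-squared belong in the plan, but they do not answer the differently worded hypothesis in the Specific Aims.
- **Aim 1 already plans part of this**: a cutoff for normal swallows and held-out accuracy, with PAS 1-2 as the expected outcome. This stands for that one boundary. A reader might infer that Aim 3 will receive no tested cutoff at all. The documents do not support that, because A3.d draws on Aim 1 as well. MBSImP, residue and higher severity levels remain uncovered.
- **The metrics are examples and the primary method is ordinal.** This also stands. A reader might infer that A2.e judges only regression-translated scores. In fact regression trees and linear mixed models are additional, and no squared-error loss is stated for the primary model. But no ordinal or cutoff metric is named, and the benchmark and power rest on the same two measures.
- **The illustration depends on its assumptions.** Nothing says the VF cutoff would be carried over unchanged. At an assumed R² of 0.5 with 20% impaired, doing so gives 39%/95% sensitivity/specificity, against 79%/74% for a cutoff chosen by the Youden index. Both are points on one ROC curve, so this shows a different trade-off and not a worse model; 0.5 is not a plan figure either.
- **Aim 3's main comparison uses c-statistics** (A3.e), which monotone shrinkage of a single score leaves unchanged. A fixed criterion matters for the screening strategies in A3.a.

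**Conclusion.** The point holds as a gap between hypothesis and analysis. The Specific Aims hypothesis for Aim 2 has no VF cutoff, no HRCA cutoff and no test in A2.d to A2.h, and the quantities that define success there can be met or be significant without answering it. This rests on the text alone and would remain true with a near-perfect fit.

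The numerical size is illustrative. Under a bivariate-normal model with 36% impaired and the VF cutoff applied to a least-squares score, sensitivity is about 11% at the powered R-squared of 0.06. It is about 84% to 94% if the RMSE benchmark is met with a PAS SD of 1 to 2.5. The documents report no achieved R-squared.

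Two further inferences should not be drawn. Least-squares predictions shrink toward the mean of the data set, not toward normal as such, and by an amount set by R-squared. And although a mixed model with an uninformative HRCA predictor can show a training R-squared near 0.72 at an intraclass correlation of 0.7 when person effects are counted, nothing says the plan would report it that way. A2.h frames R-squared around 20 predictors in a linear model.

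This should be corrected before the Aim 2 analysis. It does not invalidate the data collection.

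**What to change.** In A2.e:

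1. Name the VF cutoffs: PAS 1-2 against 3-8, consistent with A1.f and A2.c, plus prespecified MBSImP and residue cutoffs.
2. For each, choose the HRCA cutoff in the training persons by a stated rule (for example from the ROC curve) and lock it. Keep all swallows of one person on the same side of the split.
3. In the validation persons, report sensitivity and specificity with person-clustered confidence intervals, and weighted kappa for agreement on the ordinal scales.
4. State that this is the test of the Specific Aims hypothesis, and align A2.f and A2.h with it.
5. Keep RMSE and R-squared as descriptive measures of score translation for the A2.a working hypothesis, computed from predictions that do not use person effects.

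The cost is a little more analysis and some prespecification. No new patients, recordings or ratings are needed.

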### AIM 3: Prospectively assess the accuracy of our HRCA system in predicting clinically significant dysphagia and aspiration in a randomized, controlled trial.

**A3.a. Introduction:** For Aspirometer-based swallowing screening to be useful in clinical settings, it needs to outperform SIS in identifying patients at risk of silent aspiration and clinically significant dysphagia before they are placed at risk of aspiration pneumonia, or its further development is not warranted. The objective of this aim is to establish the superiority of dysphagia screening with the Aspirometer to the existing non-instrumental SIS protocols. To attain the objective of this aim, we will test the working hypothesis that the Aspirometer combined with, and independent of, SIS will identify VF-confirmed clinically significant OPD more accurately than SIS alone. We will use an approach that screens consenting patients with ordinary SIS and HRCA, and compare four levels of screening predictions (SIS human judgment criterion only, HRCA criterion only, SIS and HRCA criteria, SIS or HRCA criteria) for identifying dysphagia as measured from gold standard VF testing of all participants performed within 24 hours of screening. The rationale for this aim is that a clinically useful and accurate HRCA-based instrumental screening method not only needs to be rigorously tested against current practices to establish its validity and accuracy, but also needs to be examined for possible incorporation into current clinical practices. The acquisition of such knowledge is critical to the improved mitigation of unnecessary and adverse health sequelae associated with OPD. Based on our preliminary data, we expect that HRCA-based screening will be able to identify (sensitivity=) 90% or more of patients with OPD needing intervention or follow-up with gold standard VF testing and (specificity=) 90% of those not needing VF testing using one of the 3 strategies incorporating HRCA. This would validate the development of HRCA-based swallow screening tools that pre-emptively identify patients with a high pneumonia risk due to OPD, expedite intervention or gold standard swallowing diagnostic tests when necessary, and to reject the need for VF testing when unnecessary.

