### **A3.d. Experimental approach:** The main goal of this aim is to demonstrate that the proposed HRCA tool is objective and can improve upon the accuracy of SIS alone in identifying participants who have OPD and need to undergo a VF exam or need immediate intervention (Figure 11). To achieve this goal, we will carry out the following experimental steps:

STEP 1: Enroll 50 consenting patients eligible for SIS in the experiment, and perform combined SIS screening and an HRCA screening. STEP 2: The HRCA system will be applied to all patients. The dysphagia SIS screen employed in the University of Pittsburgh Medical Center Presbyterian University Hospital will be performed, which consists of two or three 5mL water swallows and drinking 90mL of water at a self-selected pace. STEP 3: Nurses or other staff (non-SLPs or physicians) administering the screens and blinded to the HRCA output, will score the screens on the basis of the institutional SIS algorithm, denoting any signs of OPD or penetration/aspiration (e.g., wet voice, coughs) for each swallow that is observed. For the concurrent HRCA screening, we will record and denote the output of the algorithm for each observed swallow with findings from Aims 1 & 2. STEP 4: We will administer a VF exam for all patients using clinical protocols that include the same bolus conditions (5mL thin liquid, 30mL thin liquid) of swallowed material used in the SIS, within a 24-hour period to confirm the presence or absence of dysphagia/aspiration. STEP 5: The MBSImP, the PAS and the Normalized Residue Ratio Scale will be used to measure swallow impairment, airway protection and post-swallow pharyngeal residue. These measures will be made by our trained laboratory associates. STEP 6: HRCA, SIS, and VF results will be compared.

**Table 4 –** HRCA-based screening can detect aspiration, validated against concurrent VF. SENS = Sensitivity; SPEC = Specificity; FPR = False Positive Rate; FNR = False Negative Rate; PB = Per bolus; PP = Per participant.

Parameter	Statistic	PB	PP
Impaired Swallowing Safety (13/40 patients; 55/154 swallows)	SENS	90%	100%
	SPEC	77%	54%
	FPR	23%	48%
	FNR	10%	0%

**Figure 12 –** Our proposed experimental and data analysis approach for Aim 3.

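### Aim 3 is called a randomized trial but is a single-group paired accuracy study, and its only planned test cannot support the two-part hypothesis in the Specific Aims

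*Combined protocol and SAP*

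**What the plan says.** **Design label.** The Aim 3 heading places the assessment of HRCA "in predicting clinically significant dysphagia and aspiration in a randomized, controlled trial". The Specific Aims use the same label, as do Innovation Table 1 and the closing lines of that section.

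**Procedure.** A3.d STEP 1 reads "Enroll 50 consenting patients eligible for SIS in the experiment, and perform combined SIS screening and an HRCA screening". STEP 2 adds "The HRCA system will be applied to all patients", and STEP 4 "We will administer a VF exam for all patients using clinical protocols". The staff who score SIS are blinded to HRCA output. The text gives no arms, ratio, sequence or concealment. The Specific Aims themselves plan to "compare all screening predictions (SIS, HRCA, SIS + HRCA) to VF data from all participants".

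**Hypotheses.** There are two.
- The Specific Aims require significance on both OPD and non-OPD detection: "in a randomized, controlled trial. Hypothesis: HRCA, will detect significantly more OPD and significantly more non-OPD, compared to SIS alone".
- A3.a asks only whether the Aspirometer, with or without SIS, "will identify VF-confirmed clinically significant OPD more accurately than SIS alone". It also expects sensitivity of at least 90% and a specificity of "90% of those not needing VF testing using one of the 3 strategies incorporating HRCA", with no test attached to either figure.

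**Analysis and power.** A3.e fits logistic models and compares their c-statistics by DeLong's method. STEP 6 of A3.d says the results are to be compared but names no test. A3.h states 80% power for an AUC gain of 0.240 over an SIS value of 0.600, with 46 analysed patients, 50% prevalence, an SIS–HRCA correlation of 0.3 and alpha 0.05.

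**The concern.** The label tells readers that patients are allocated to screening strategies, when each patient serves as their own comparator. That does not damage the accuracy comparison, and pairing is efficient here, but it misdescribes the evidence.

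The second mismatch bears on the conclusion. For a pass/fail screen, c = (sensitivity + specificity)/2, so a gain in c may come wholly from specificity. Missed silent aspiration is the stated reason for the device. A3.b describes existing screens as strong on sensitivity and weak on specificity, which is the setting in which a specificity-driven gain is most likely. Under the plan, a significant c-statistic could be reported as confirming the Specific Aims hypothesis although neither component had been tested.

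**Working it through.** **1. The plan's own figure.** Take 46 × 50% = 23 patients per VF class, AUCs 0.600 and 0.840, two-sided alpha 0.05, and 0.3 read as the correlation between the two AUC estimates. The Hanley–McNeil variance is [A(1−A) + 22(A/(2−A) − A²) + 22(2A²/(1+A) − A²)]/23².
- A = 0.600 gives 0.00705; A = 0.840 gives 0.00358.
- Variance of the difference: 0.00705 + 0.00358 − 2(0.3)√(0.00705 × 0.00358) = 0.00761, so SE = 0.0872.
- Power = Φ(0.240/0.0872 − 1.96) = Φ(0.79) = 78.5%.

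This is within 2 points of the stated 80%. The calculation is for a paired single group, which confirms the design reading. At a correlation of 0.26–0.28, power is 76–77%.

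**2. What the two-part hypothesis needs.** It needs a paired test of sensitivity in the 23 VF-positives and of specificity in the 23 VF-negatives, both significant in favour of HRCA. Three assumptions are not in the documents: the split of SIS c = 0.600 into sensitivity and specificity, the within-class correlation r, and the reading of 90%/90% as HRCA alone on a pass/fail basis.

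Example: SIS 60%, HRCA 90%, r = 0.
- P(only HRCA right) = 0.9 × 0.4 = 0.36; P(only SIS right) = 0.6 × 0.1 = 0.06.
- Exact two-sided McNemar power with 23 patients is 0.521. The two classes are independent, so joint power is 0.521² = 0.272.
- At r = 0.3 the figures are 0.662 and 0.438.

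**3. DeLong beside the two-part test.** For pass/fail results, the change in c is half the sum of the sensitivity and specificity differences. Its variance is (s₁²/23 + s₀²/23)/4, where s² is the variance of the paired differences in each class. Exact enumeration of the discordant pairs gives the table below. Triplets are exact / mid-p / asymptotic McNemar.

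| SIS sens/spec | HRCA | r | DeLong significant | Both McNemar significant | Share of significant DeLong results lacking both |
|---|---|---|---|---|---|
| 60/60 | 90/90 | 0 | 93.8% | 27.2 / 39.8 / 40.4% | 71.0 / 57.6 / 56.9% |
| 60/60 | 90/90 | 0.3 | 99.2% | 43.8 / 62.0 / 68.7% | 55.8 / 37.5 / 30.7% |
| 60/60 | 84/84 | 0 | 75.0% | 9.3 / 16.1 / 16.3% | 87.6 / 78.5 / 78.3% |
| 60/60 | 84/84 | 0.3 | 89.3% | 15.3 / 27.4 / 30.9% | 82.8 / 69.3 / 65.3% |
| 50/40 | 90/90 | 0 | 99.9% | 72.1 / 81.3 / 81.4% | 27.8 / 18.6 / 18.5% |
| 50/40 | 90/90 | 0.3* | 100.0% | 92.2 / 96.7 / 97.8% | 7.8 / 3.3 / 2.2% |

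*For a 40%/90% pair the largest attainable correlation is √(0.4 × 0.1/(0.6 × 0.9)) = 0.27, so that value is used for specificity. The same cap applies to 80/40 below. The 50/40 row is the worst case in the opening paragraph of the Specific Aims; its c is 0.45, below A3.h's 0.600.

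**4. When the conclusion would be wrong in direction.** The share of significant DeLong results with observed HRCA sensitivity no higher than SIS (HRCA 90/90, r from 0 to 0.3) is:
- under 1% for SIS 60/60;
- 2–4% for SIS 70/50;
- 18–20% for SIS 80/40.

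All three SIS splits have c = 0.600. A sharper case with A3.h's two AUCs is SIS 80/40 against HRCA 78/90, where (78 + 90)/2 = 84 and HRCA is truly less sensitive. At r = 0.15, DeLong is significant in 85% of studies and both McNemar tests in 0.4%.

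**5. Table 3 screens against HRCA 90/90.** At 100% sensitivity HRCA cannot detect more OPD, yet DeLong (r = 0) is significant in 95% (specificity 29%), 73% (44%), 59% (50%) and 24% (64%) of studies. For the 92/66 screen it is 35% (45% at r = 0.3).

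**6. Continuous HRCA score.** An equal-variance binormal curve through 90/90 has c = Φ(2 × 1.2816/√2) = 0.965. With SIS 60/60, r = 0 and 40,000 simulations, DeLong is significant in 99.8% of studies, and 60–73% of those lack the two-part result.

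**The case against.** The detailed Aim 3 section is coherent on its own terms: overall accuracy in A3.a, c-statistics in A3.e and AUC power in A3.h. On that view the Specific Aims sentence is only a summary worded too strongly. That DeLong suits the A3.a hypothesis is accepted. The stronger claim nevertheless stands in the plan, demands significance on both parts, and has no test.

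The large percentages at 60/60 mainly reflect the low power of McNemar tests on 23 patients. HRCA truly is better on both components there, and among significant DeLong results both observed components favour HRCA in more than 99%. This is correct, so those percentages should not be read as error rates. They show that the claimed significance would not have been demonstrated. The direction-of-effect figures in step 4 are the better measure of harm.

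The Table 3 screens imply c of about 0.65 to 0.82, above the planning value of 0.600, and the trial uses the hospital's own SIS. This also stands: step 5 is conditional on that SIS behaving like the published ones. The 80/40 split needs no such departure from c = 0.600.

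A3.e may use a continuous HRCA score, whereas most of the scenarios are pass/fail. Step 6 gives a similar answer, but for only one curve and one SIS split.

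The Aim 3 design figure is not in the copy reviewed. The text of A3.d nevertheless applies every procedure to all patients.

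**Conclusion.** The concern holds on both parts and should be fixed. The randomized label conflicts with A3.d; this is a matter of description and leaves the paired comparison valid. The two-part hypothesis in the Specific Aims is untested by A3.e, and a significant c-statistic does not establish it.

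The size depends on an SIS split that the documents do not give. It is small if SIS is as weak as the opening of the Specific Aims says, and large if SIS has the high sensitivity and low specificity described in A3.b. With 46 patients, joint power for the two-part claim at SIS 60/60 and HRCA 90/90 is 27–44% (exact), 40–62% (mid-p) or 40–69% (asymptotic).

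**What to change.** 1. **Label.** In the Specific Aims, Innovation (Table 1 and closing lines) and the Aim 3 heading, describe a prospective paired diagnostic-accuracy study with SIS as concurrent comparator. If some allocation is intended, A3.d must describe it.
2. **Hypothesis and test: choose one.**
   - Reword the Specific Aims hypothesis to the overall-accuracy form in A3.a. This costs only wording but gives up the claim of both more OPD and more non-OPD.
   - Keep the two-part claim and add to A3.e paired McNemar tests of HRCA alone against SIS: sensitivity in VF-positives and specificity in VF-negatives, both required. Choose exact or mid-p in advance and lock the HRCA cutoff before Aim 3 data are seen. DeLong stays for the A3.a hypothesis.
3. **AND and OR rules.** If reported as pass/fail, give paired sensitivity and specificity with exact confidence intervals and do not require superiority on both. AND cannot exceed SIS in sensitivity, and OR cannot exceed it in specificity.
4. **Power.** If the two-part test is kept, report its joint power in A3.h under the sponsor's own stated SIS and HRCA values.

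The added tests use data already being collected, and n can stay at 50 recruited if the lower joint power is disclosed. Reaching 80% joint power with exact tests at 60/60 against 90/90 would need about 92 analysed patients (r = 0) or 68 (r = 0.3).
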